Appendix II: Study Screening Log

STANCE Screening Log

Site: _____

Investigator: _____

Screening Number	Gender	Screening Date	Screening Status (use codes below)	Consent Obtained	Enrolled	IF NOT ELIGIBLE, indicate reason(s) from codes below	Study ID # (if Enrolled) Site-Subject Ex. 01-001	Date Enrolled
□ □ □ □	 M  F	/ / mm/dd/yyyy	 1  2  3  4	 Yes  No	 Yes  No	 1  2  3		/ / mm/dd/yyyy
□ □ □ □	 M  F	/ / mm/dd/yyyy	 1  2  3  4	 Yes  No	 Yes  No	 1  2  3		/ / mm/dd/yyyy
□ □ □ □	 M  F	/ / mm/dd/yyyy	 1  2  3  4	 Yes  No	 Yes  No	 1  2  3		/ / mm/dd/yyyy
□ □ □ □	 M  F	/ / mm/dd/yyyy	 1  2  3  4	 Yes  No	 Yes  No	 1  2  3		/ / mm/dd/yyyy
□ □ □ □	 M  F	/ / mm/dd/yyyy	 1  2  3  4	 Yes  No	 Yes  No	 1  2  3		/ / mm/dd/yyyy
□ □ □ □	 M  F	/ / mm/dd/yyyy	 1  2  3  4	 Yes  No	 Yes  No	 1  2  3		/ / mm/dd/yyyy
□ □ □ □	 M  F	/ / mm/dd/yyyy	 1  2  3  4	 Yes  No	 Yes  No	 1  2  3		/ / mm/dd/yyyy
□ □ □ □	 M  F	/ / mm/dd/yyyy	 1  2  3  4	 Yes  No	 Yes  No	 1  2  3		/ / mm/dd/yyyy

Screen Status Codes:

1-Eligible

2-Eligible, declined participation

3-Not Eligible

4- Other, specify in space provided

If not eligible,
Reason:

1-Inclusion # (specify)

2-Exclusion # (specify)

3-Other (specify)

- **Appendix III: Study Drug Accountability Log**

STANCE Trial – Study Drug Accountability Record		PAGE NO.
Name of Institution:		Protocol Number: CUMC AAAM2407 /
Drug Name: (atorvastatin, simvastatin, rosuvastatin v. placebo)		Dose Form and Strength: capsules atorvastatin 80 mg vs. placebo; simvastatin 40 mg vs. placebo; rosuvastatin 20 mg vs placebo; atorvastatin 10 mg vs. atorvastatin 80 mg
Protocol Title: Statin Neuroprotection and Carotid Endarterectomy: Safety, Feasibility and Outcome (STANCE)		Dispensing Area: Research Pharmacy
Investigator Name:		Investigator or site Number

Line No.	Date	Participant's ID No.	ARM 2 or 3	Quantity Dispensed Or Received (128-128-54 capsules)	Bottle Number	Rcpt / Disp Recorded By	Date Returned	Qty Return (capsules)	Qty Destroyed (capsules)	Date Destroyed	Recorder's Initials
1.											
2.											
3.											
4.											
5.											
6.											
7.											
8.											
9.											
10.											
11.											
12.											
13.											
14.											
15.											
16.											
17.											

HRPP/QIP/QIU Web Postings\investigational-agent-accountability-record.doc

• Appendix IV: Protocol Deviation Log (for subject binders)

STANCE Trial Protocol Deviations Log

Site Number: _____ Pt_ID: _____	Visit Date: ____/____/____ 
 m m d d y y y y 

--	--

Did this participant have any protocol deviations? ☐ Yes ☐ No

Description of Protocol Deviation:	Deviation Category*	Deviation Code**	Date Deviation Occurred: (mm/dd/yyyy)	Date IRB Notified (if applicable):	Principal Investigator's Signature	Date Signed (mm/dd/yyyy)

STANCE Protocol Deviations

Page ____ of ____

Version 1.0

***DEVIATION CATEGORIES:**

- A. Safety
- B. Informed Consent
- C. Eligibility
- D. Protocol implementation
- E. Other, specify in log

****DEVIATION CODES:** Numbers listed by the sample protocol deviations

Safety (Category A)

- 1. Not reporting an SAE within 24 hours
- 2. Laboratory tests not done
- 3. AE/SAE is not reported to IRB
- 4. Other, specify in log

Informed Consent (Category B)

- 5. Failure to obtain informed consent

- 6. Consent form used was not current IRB-approved version
- 7. Consent form does not include updates or information required by IRB
- 8. Consent form missing
- 9. Consent form not signed and dated by participant
- 10. Consent form does not contain all required signatures
- 11. Other, specify in log

Eligibility (Category C)

- 12. Participant did not meet eligibility criterion
- 13. Randomization of an ineligible participant
- 14. Participant randomized prior to completing Baseline Assessment, etc.
- 15. Randomization and/or treatment of participant prior to IRB approval of protocol
- 16. Other, specify in log

Protocol implementation (Category D)

- 17. Failure to keep IRB approval up to date

- | | |
|---|---------------------------|
| 18. Participant receives wrong treatment | 22. Missed assessment |
| 19. Participant seen outside visit window | 23. Missed visit |
| 20. Use of unallowable concomitant treatments | 24. Other, specify in log |
| 21. Prescribed dosing outside protocol guidelines | |

- **Appendix V: Primary Medical Doctor Letter:**

**Statin Neuroprotection and Carotid Endarterectomy:
Safety, Feasibility and Outcomes" (STANCE)**
Columbia University Medical Center
Department of Neurological Surgery
[name]
[name]

[date]

RE: [name]

Dear Doctor [name of PMD]:

DOB: [DOB]

This letter is to inform you that your patient has elected to take part in a research study entitled, Statin Neuroprotection and Carotid Endarterectomy: Safety, Feasibility and Outcomes" (STANCE). The study is sponsored by the National Institutes of Aging (NCT02850081) and is being conducted at multiple sites in the US including Columbia University Medical Center.

This is a phase III study for asymptomatic patients with carotid artery stenosis designed to assess if maximizing statin doses for approximately two weeks (12-18 days) prior to carotid endarterectomy (CEA) is neuroprotective. Patients who are already on the maximal statin dose of either atorvastatin (80 mg), simvastatin (40 mg) or rosuvastatin (20 mg) will remain on their current doses and will be part of our observational arm. The patients that are currently on sub-maximal daily doses of the previously mentioned statins will be randomized to either 1) their current dose plus placebo or 2) their current dose plus the necessary milligrams needed to bring them to the FDA approved maximal dose per day for their corresponding statin. Those patients who are statin naïve, 30 days prior to enrollment, will be randomized to daily doses of either 1) 10 mg of atorvastatin or 2) 80 mg of atorvastatin.

We will stay in contact with Mr./Mrs. _____ via phone calls prior to the CEA to assure study drug compliance and safety. We will also assess him/her prior to the CEA, 12-25 hours post-CEA, and during their post-operative clinical visit (approximately at 30 days post-CEA) for early cognitive dysfunction (eCD). The final follow-up phone call will be one year after their CEA procedure.

We have attached a copy of your patient's study consent form. We ask that you not alter your patient's assigned statin dose unless it is clinically necessary. If you do change their dose prior to their CEA, please let us know. After their CEA, Mr./Mrs. _____ will be prescribed statins as per the standard of care for post-CEA patients by their treating physician and will not receive any further study drugs.

If you have questions, please do not hesitate to contact our Study Clinical Coordinator, [name of coordinator] at [contact number] or one of us.

Sincerely yours,

[Contact Information for Principal Investigator at Site]

• Appendix VI: Delegation of Authority Log

STANCE TRIAL
SITE PERSONNEL SIGNATURES & DELEGATED RESPONSIBILITIES LOG

Study Site: _____

NAME (PRINT OR TYPE)	SIGNATURE	INITIALS	STUDY ROLE (i.e. Site PI, Study physician, sub-investigators, Study Coordinator, Research Pharmacy, etc)	DELEGATED RESPONSIBILITIES* (list all that apply A-I)	DATES (Involved in STUDY) (mm/dd/yyyy)	PI Initials/Date (mm/dd/yyyy)
					Start: _____ Stop: _____	
					Start: _____ Stop: _____	
					Start: _____ Stop: _____	
					Start: _____ Stop: _____	
					Start: _____ Stop: _____	
					Start: _____ Stop: _____	
					Start: _____ Stop: _____	
					Start: _____ Stop: _____	
					Start: _____ Stop: _____	

Delegated Responsibilities:

A = Make eligibility decisions	B = Obtain informed consent	C = Rx Study Drug from Research Pharmacy
D = CRF completion/correction	E = Baseline/follow-up evaluations	F = Evaluate and monitor for adverse events
G = Pick up Study Drug Res Pharmacy	H = Query resolution	I = Maintain Regulatory Binder
J = Train Study Sites in NP measures	K = Monitor Study Sites	L = Research Pharmacy at Site M=Other: _____

Version date: 1/20/2017

Page ____ of ____

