We have defined our primary outcome on Z-scores based on the mean and standard deviation of cognitive testing change in scores of a surgical reference group before and after surgery (24h and approximately 30 days post-op OR when the patient returns for their post-CEA clinical visit). The cognitive testing was divided by cognitive domains and the patients were considered to have postoperative early cognitive dysfunction (eCD) based on two criteria to account for

both focal and global/ hemispheric deficits. Consequently, anyone with: (a) ≥ 2 SD worse than reference group in two or more cognitive domains or (b) ≥ 1.5 SD worse than the reference group in all cognitive domains tested will be considered a primary outcome. If the subjects experience stroke or TIA peri-operatively, they will be considered as having reached a secondary outcome in the study.

Interventions and Duration

Participant subjects who are already on the maximal statin dose of either atorvastatin (80 mg), simvastatin (40 mg or 20 mg + amlodipine) or rosuvastatin (20 mg) will remain on their current statin doses and will be part of our observational arm (ARM 1). The subjects that are currently on sub-maximal daily doses of the previously mentioned statins will be randomized to their current dose plus placebo or their current dose plus the necessary milligrams needed to bring them to the FDA approved maximal dose per day for their corresponding statin (ARM 2). Those subjects who are statin naïve, 30 days prior to enrollment, will be randomized to daily doses of either 10 mg of atorvastatin or 80 mg of atorvastatin (ARM 3).

We will stay in contact with the subjects via phone calls prior and post their CEA to assure study drug compliance and safety. We will also assess them prior to their CEA, 12-25 hours post-CEA for early cognitive dysfunction (eCD) and during their post-operative clinical visit (approximately at 30 days post-CEA) for delayed cognitive dysfunction (dCD). The final follow-up phone call will be one year after their CEA procedure.

Sample Size and Population

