2.2.1 Hypothesis

While there are several non-modifiable risk factors for eCD after CEA identified from previous research, including medically treated diabetes mellitus and the presence of the ApoE-ε4 genotype, we have only been able to identify one potentially neuroprotective factor, namely preoperative statin use. Consequently, we hypothesize that in CEA patients:

- 1) A pre-operative statin regimen is protective against eCD (12-25h) and dCD (30d); consequently, early (365d) mortality.
- 2) Maximal doses may be essential in achieving optimal neuroprotection against eCD and dCD, with lipophilic statins or those that pass the blood-brain barrier more easily achieve similar effects at lower doses.

3 **STUDY DESIGN**

[figure not shown]
This is a Phase 3, multicenter, observational (ARM 1), randomized and double-blind study (ARM 2 and ARM 3), and placebo-controlled (ARM 2), where 1,000 carotid stenosis outpatient participants will be assigned to a specific daily statin regimen of no fewer than 2 and no greater than 18 doses prior to their CEA.

We will include patients who are either statin naïve, assuming no history of adverse experience with a statin, or on one of three types of statins: simvastatin, atorvastatin, or rosuvastatin. Patients will be enrolled, and based on their preexisting statin regimen, they will be grouped into one of three arms prior to CEA: ARM 1) Patients on a pre-existing maximal daily dose statin regimen will be observed, ARM 2) Patients on a pre-existing statin regimen at sub-maximal doses will be randomized to maintain their current dose plus placebo or current dose plus the necessary milligrams to reach maximal daily dose, and ARM 3) Patients who are on no preexisting statin regimen, statin naïve in the last 30 days, will be randomized to atorvastatin

10mg or atorvastatin 80mg for no fewer than 2 and no greater than 18 daily doses before their CEA (Figure 6).

As per the simvastatin drug insert, patients taking amlodipine (Norvasc) should not exceed 20 mg of simvastatin; therefore, we will only potentially increase any patient who is also on amlodipine to daily doses of 20 mg and not 40 mg. Consequently:

- *If subject is on 40 mg simvastatin without amlodipine – they will be in ARM 1 (observational)
- *If subject is on 40 mg simvastatin + amlodipine – they will be in ARM 1 (observational)

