- *If subject is on 20 mg simvastatin + amlodipine – they will be in ARM 1 (observational) *If subject is on < 40 mg of simvastatin without amlodipine, they will be in ARM 2 and potentially randomized to 40 mg of simvastatin daily.
- *If subject is on < 20 mg of simvastatin + amlodipine, they will be in ARM 2 and potentially randomized ONLY to 20 mg of simvastatin daily not 40 mg.

All potential participants will be pre-screened for eligibility prior to offering them participation in the study. Once informed consent has been obtained, the final screening process to screen out those who may already have mild cognitive impairment (MCI) from the study will consist of the Montreal Cognitive Assessment (MoCA ≤ 25 = abnormal) and the Ascertain Dementia 8-item Informant Questionnaire (AD8 ≥ 2 = abnormal). If both assessments are not within normal ranges, these patients will not be randomized or assigned to the observational arm. Those with baseline MCI will be screened out from the study and not followed.

All of the potentially eligible subjects will be documented in the Study Screening Log (see Appendix III) and the logs will be collected monthly by the Central Coordinating Center at CUMC.

[figure not shown]
The randomization design is stratified by center, previous use of statin and in random blocks of 4 and 6. After the participant completes the screening process, ARM 2 and ARM 3 will be randomized using a centralized, secure web-based system created and managed by the Statistical Analysis Center (SAC) at the Mailman School of Public Health at Columbia University.

The study personnel will request the study drug from the site's Pharmacy/Research Pharmacy and provide the participant with the study drug instructions and corresponding amount of study drug capsules to take during their dosing period. The participants will self-administer the assigned daily doses of study statin and keep a Study Medication Compliance form (diary) of all doses taken, including their current statin doses, and the reasons for any missed dose(s) from enrollment to the day of their CEA. On the day of CEA, the remaining study drug capsules will be counted and the Study Drug Log will be collected to assess compliance.

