4.2 Exclusion Criteria

- 1) Patient has underlying disease other than atherosclerosis (i.e. autoimmune disease, known active malignancy).

- 2) Patient has documented dementia or screens out based on abnormal Baseline MoCA (≤ 25) and AD8 (≥ 2).
- 3) Patient's life expectancy is < 12 months.
- 4) Patient has advanced renal failure (serum creatinine > 2.5 mg/dL)
- 5) Patient has evidence of severe congestive heart failure or has history of end-stage cardiovascular disease (e.g. CHF NYHA Class III or IV or unstable angina).
- 6) Patient has history of intolerance or allergic reaction to any statins (myotoxicity, hepatic dysfunction, rash, etc.) – unless they would be in the Observational Arm (Arm 1) and therefore will not be receiving any study drug.
- 7) Patient has received an investigational drug within 30 days.
- 8) Patient is pregnant or lactating.
- 9) Except those eligible for the Observational Arm who do not receive any study statin, patient who is currently taking any of the following which have been shown to interact with atorvastatin and/or simvastatin and/or rosuvastatin (as per current drug package inserts):
 - *Cyclosporine;
 - *HIV Protease Inhibitors/Antivirals (e.g. roatanavir or plus roatanavir, tipranavir, lopinavir, boceprevir, saquinavir, darunavir, fosamprenavir, nelfinavir, efavirenz/tenofobir, atazanavir, simeprevir);
 - *Hep C Protease Inhibitor/Antivirals (e.g. telaprevir);
 - *Antibiotics (i.e. cobicistat-containing products like Tybost, rifampin/rifampicin, clarithromycin, telithromycin, erythromycin);
 - *Anti-fungals (i.e. itraconazole, ketoconazole, posaconazole, voriconazole, fluconazole); *Gemfibrozil; Other Fenofibrates (e.g. Tricor, fibric acid);
 - *Niacin > 1 g/day or statins in combination with niacin (e.g. Vytorin, Simcor);
 - *Colchicine;
 - *Danazol;
 - *Calcium Channel Blockers: Diltiazem, Varapamil;
 - * Dronedarone;
 - *Amiodarone;
 - *Digoxin;
 - *Ranolazine;
 - *Nefazodone;
 - *Warfarin/Coumadin;
 - *Lomitapide;
 - *Grapefruit juice (subject must be willing to avoid grapefruit juice).

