on 5 mg of Simvastatin, then they will need to add 7 capsules/day to potentially reach 40 mg of active drug unless they are also on amlodipine and then they will only potentially be optimized to 20 mg for safety.)

- **Rosuvastatin vs Placebo (each study capsule = 5 mg)**

- 54 capsule count bottle
 - Coordinator will write on the label how many capsules they need to take when they take their statin drug each day (example: If subject is on 5 mg of rosuvastatin, then they will need to add 3 capsules/day to potentially reach 20 mg of active drug)

ARM 3: Subjects that are statin naïve (no statins in the past 30 days) will be randomized to receive either 10 mg or 80 mg of atorvastatin during the dosing period.

- 18 capsule count bottle
- Subjects will take 1 (one) capsule/day

Patients who will be treated with invasive transcarotid artery revascularization (TCAR) procedures that use a special transcarotid neuro-protection system (NPS) will be excluded.

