5.3.1 Allowed Interventions

Concomitant therapy with any of the following is allowed as long as the exclusion criteria described in Section 4.2 are observed:

- Medications necessary for treatment of AEs according to the discretion of the Investigator.
- Medications used in standard of care to treat CEA patients, cardiovascular risk factors, or other comorbid conditions.

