7 SAFETY ASSESSMENTS

7.1 Clinical Risks

Patients will have clinical laboratory tests upon enrollment and a research coordinator or nurse will contact them 3 days after starting the study drug to verify the patient's complying with the statin regimen as well as to ask questions regarding their subjective experience of taking the study assigned statin regimen (if the CEA does not occur prior to day 3). If the CEA does happen prior to day 3, the Day of CEA Safety Questionnaire will verify compliance and ask about the subjects experience with the assigned statin regimen. Patients will be asked about a variety of symptoms associated, though rarely, with statin use. According to the FDA, the value of statins has been clearly established yet they also advise that statins,

including the ones which will be part of this study (i.e. simvastatin, atorvastatin and rosuvastatin) offer some rare, but potential risks to statin users:¹

- Hepatic toxicity (indicator symptoms: elevated liver enzymes, bleeding or jaundice)
- Muscle toxicity (indicators symptoms: myalgia and arthralgia)
- Increased glucose levels

In addition, from clinical practice, we also know that statins may produce some minor gastrointestinal discomfort; however, these are minor and mostly tolerated as the benefit of statins tends to outweigh the minor stomach upsets they may produce in some individuals.

Patients randomized to maximize their statin regimen or randomized into the atorvastatin 80mg group are the only patients we anticipate having any risk of side effects.

If a patient reports subjective experiences of side effects, their statin regimen will be modified at the discretion of the caring physician. Although the randomization of the patient is compromised, we will continue to evaluate that patient and proceed with intention to treat principles. If the laboratory values the morning of surgery present with elevations in CK or LFT, their statin regimen will be modified at the discretion of the caring physician.

Other Potential Study Procedure Risks:

- Some people may feel uncomfortable taking cognitive tests.
- Slight pain and/or temporary discoloration of the skin after blood draws.
- Unlikely, but potential breach of confidentiality

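### The 20 mg simvastatin limit with amlodipine is applied only at entry: no step re-applies it if amlodipine is started before CEA, and the doctor letter omits it

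*Combined protocol and SAP*

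**What the plan says.** Section 3 cites the simvastatin insert for the limit: "patients taking amlodipine (Norvasc) should not exceed 20 mg of simvastatin". It then sorts patients by amlodipine use at entry. Those on simvastatin 20 mg with amlodipine go to the observational arm. For those on less than 20 mg with amlodipine, "they will be in ARM 2 and potentially randomized ONLY to 20 mg of simvastatin daily not 40 mg". Section 5.1 applies the same limit when the coordinator writes the daily capsule count on the label: the target is 40 mg "unless they are also on amlodipine and then they will only potentially be optimized to 20 mg for safety".

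On other drugs, Sections 4.2 and 5.3.3 carry the same entry for this class, "Calcium Channel Blockers: Diltiazem, Varapamil". Amlodipine is not named. Provided the exclusion criteria are observed, Section 5.3.1 allows "Medications used in standard of care to treat CEA patients, cardiovascular risk factors, or other comorbid conditions".

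The Precis keeps the amlodipine exception when it defines the maximal dose: "atorvastatin (80 mg), simvastatin (40 mg or 20 mg + amlodipine) or rosuvastatin (20 mg) will remain on their current statin doses". The matching sentence in the doctor letter (Appendix V) does not: "Patients who are already on the maximal statin dose of either atorvastatin (80 mg), simvastatin (40 mg) or rosuvastatin (20 mg) will remain" on those doses. The letter asks the doctor to leave the assigned statin dose alone unless there is a clinical need, and to tell the study team if that dose is changed before CEA. It does not ask about new drugs that interact with the statin.

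**The concern.** The limit depends on a second drug that can be started at any time, yet the plan checks for that drug only at entry. An Arm 2 patient enrolled without amlodipine and randomised to active simvastatin is taken to a total of 40 mg. If a doctor then prescribes amlodipine before surgery, the patient is above a limit that the protocol itself describes as a safety measure. The excess comes from blinded study capsules, so the doctor's own record shows only the prescribed dose, which may be within the limit.

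The letter is the study's direct channel to that doctor, and Section 7.2.1 presents it as protection against duplicated or unknown statin dosing. A warning about amlodipine belongs there. What is at stake is the safety of individual patients. No primary analysis figure depends on it.

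**Working it through.** The protocol gives no figure for this situation, so the check is a dose calculation followed by a trace of where the limit is enforced.

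**Dose.** Inputs from Sections 3 and 5.1: simvastatin study capsules are 5 mg, the target is 40 mg without amlodipine and 20 mg with it, and dosing runs for 2 to 18 daily doses. Capsules per day = (target − own dose) / 5. The protocol's own example reproduces: from 5 mg, (40 − 5)/5 = 7.

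| Own dose | Capsules to 40 mg | Capsules to 20 mg | Difference |
|---|---|---|---|
| 5 mg | (40 − 5)/5 = 7 | (20 − 5)/5 = 3 | 4 |
| 10 mg | (40 − 10)/5 = 6 | (20 − 10)/5 = 2 | 4 |
| 20 mg | (40 − 20)/5 = 4 | (20 − 20)/5 = 0 | 4 |

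Excess if amlodipine is added to an active 40 mg regimen: 40/20 = 2.0 times the limit. A patient on placebo capsules takes only the prescribed dose, so the study adds no excess there.

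**Where the limit is applied.**
1. Arm assignment (Section 3): by amlodipine use at entry.
2. Capsule count on the label (Section 5.1): by amlodipine use when the label is written.
3. Prohibited drugs (Section 5.3.3): amlodipine is not listed.
4. Pre-CEA calls on Days 3, 7 and 10 (Sections 5.4 and 6.2.5): medications are reviewed, but no dose action is attached.
5. Side effects (Section 7.1): "If a patient reports subjective experiences of side effects, their statin regimen will be modified at the discretion of the caring physician". The same section acts on raised CK or liver tests on the morning of surgery. Both respond to harm that has already appeared.
6. Stopping study drug (Section 8): general discretion for other medical reasons.

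Only the first two apply the 20 mg limit.

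**Window with no contact.** The last call is Day 10, give or take a day, and dosing can reach dose 18. Counting dose 1 as Day 1, the gap before a Day 18 surgery is 18 − 10 = 8 days (18 − 11 = 7 to 18 − 9 = 9 across the call window). A start in that period would be recorded on the day of CEA. A patient operated on before Day 3 receives no pre-CEA call at all.

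**Letter against protocol.** For a patient on simvastatin 20 mg with amlodipine, Section 3 says Arm 1, whereas the letter's definition makes that dose sub-maximal. For a patient on less than 20 mg with amlodipine, Section 3 allows 20 mg at most, whereas the letter implies 40 mg.

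**The case against.** The strongest reply is that Section 3 states the 20 mg figure in general terms. A patient who starts amlodipine is then a patient taking it, so continuing at 40 mg would conflict with the protocol, and the deviation list in Appendix IV has a code for dosing outside protocol guidelines. Concomitant drugs are recorded from consent onward (Section 5.3), Section 7.3 records them because statins interact with other drugs, Section 7.7 makes each site investigator responsible for safety day to day, and Section 8 allows study drug to be stopped. This stands in part. A reader might infer that the protocol directs 40 mg alongside amlodipine, and the text does not support that. What is missing is any step that puts the limit into effect after the label is written.

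A second reply is that the letter names 40 mg and gives a contact, so a careful doctor could work out that the total may be 40 mg. It would therefore be too strong to say that the doctor has no means of knowing. The letter also encloses the consent form, which was not available for this review and may mention amlodipine. Even so, the letter neither mentions the interaction nor asks to hear of a new drug.

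Third, Arm 1 knowingly includes patients on 40 mg with amlodipine. Those patients take a visible dose of both drugs outside the study's control. In Arm 2 the study adds the excess under blind.

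**Conclusion.** The point holds as a minor safety gap. The limit is stated but not carried past entry, and the letter omits it. An Arm 2 patient on active simvastatin who starts amlodipine before CEA could take up to 40 mg, 2.0 times the limit, for at most 18 doses. This assumes that neither the call review nor the investigator's discretion intervenes, which is most plausible after the last call.

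The number of patients cannot be given. A reader might try to size it from the earlier asymptomatic cohort: 66 of 94 + 66 + 12 = 172 users of the three study statins took simvastatin (38.4%), and 338 × 0.384 ≈ 130 of the increased-dose group. That estimates simvastatin users, not patients who start amlodipine before surgery, for whom the documents give no rate. The share also comes from users at any dose, while Arm 2 holds only sub-maximal users. No event count or effect on power follows.

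**What to change.** 1. **Letter (Appendix V).** Give the maximum as *simvastatin (40 mg, or 20 mg if also taking amlodipine)*. Ask the doctor to contact the study team before starting amlodipine in a patient on simvastatin, or at once if it is urgent, because the total simvastatin dose may already be 40 mg.
2. **Section 5.3.3.** For Arm 2 simvastatin patients not on amlodipine at entry, add: *if amlodipine is started before CEA, reduce study capsules by 4 per day from that day (7 to 3, 6 to 2, 4 to 0), in both groups and without unblinding.* Give the instruction by telephone and record it in the compliance form and the eCRF. The bottle stays with the patient until admission (Section 5.4), so it cannot be relabelled during a call, and the recorded date lets the pill count be read correctly.
3. **Existing calls.** Ask about amlodipine by name on Days 3, 7 and 10.

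These patients stay in the intention-to-treat analysis, as Section 7.1 already provides for modified regimens.

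The cost is IRB approval of the edits at the ten listed sites, and loss of the dose contrast for patients whose own dose is 20 mg and who start amlodipine, since their capsule count falls to zero. That matches how the protocol treats the same combination at entry, where no study drug is given.
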